1.2. Rationale for Study Design and Dose

This study includes a 29-day, open-label treatment phase in which subjects will receive tapinar of cream, 1% once daily for 29 days. Tapinarof cream has been investigated in prior studies at concentrations from 0.5% to 8.0% and at once and twice daily dosing frequencies. The 1% concentration applied once daily was chosen as the dose and dosing frequency to take forward in the clinical development program based on the data from the GSK Phase 2b clinical study in subjects with psoriasis (Study 203120). In that study, applications of tapinarof at concentrations of 0.5% and 1% applied once or twice daily were evaluated. Overall, both concentrations demonstrated an acceptable safety profile when applied once or twice daily. A once daily application regimen may reduce systemic exposure as the skin heals, thereby providing a better safety profile for a drug intended for long-term use to treat a chronic condition. Based on the efficacy and safety data from Study 203120, a regimen of 1% once daily was chosen as the tapinar of concentration and dosing frequency to be investigated in this study and intended for registration. Tapinarof has a unique PK profile whereby the highest plasma concentrations are observed in the first week of the treatment period followed by a subsequent decline to undetectable or near undetectable levels after multiple weeks of dosing. Accumulation of drug after multiple dosing has not been observed in any clinical study with tapinar of to date. The 29-day treatment phase was selected to ensure steady-state is achieved and to provide a treatment duration that allows for evaluation of safety in this population with extensive disease that has not been evaluated to date.

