3. STUDY DESIGN

3.1. Overall Design

This is a Phase 2a, multicenter, open-label study to evaluate the safety and PK of topical tapinarof cream in adults with extensive plaque psoriasis. The study will consist of three phases: Screening (up to 34 days), Treatment (29 days), and Follow-up (7-10 days).

At Day -1, eligible subjects will be enrolled into the study. During the treatment period beginning on Day 1 (Baseline), subjects will apply tapinarof cream, 1% to affected areas once a day for 29 days. Subjects will return to the clinic on Days 2, 15, 29, and 30 for study assessments and will receive a phone call on Days 8 and 22. Subjects will return to the clinic for a follow-up visit 7-10 days after the Day 29 visit. On clinic visit days, subjects will apply the study drug under the supervision of site personnel, after assessments have been completed. Full PK profiles and Holter monitoring will be collected on Day 1 and Day 29 (with corresponding 24-hour time points collected on Day 2 and Day 30, respectively). Limited PK sampling will be performed on Day 15. Pre-treatment, time-matched Holter monitoring will be conducted on Day -1 and the morning of Day 1.

Study drug will be dispensed to subjects during the clinic visits and will be administered at home between clinic visits as instructed by site personnel. Subjects will be instructed to apply study drug once daily to all affected areas, including newly appearing plaques and plaques/areas that improve during the study. Subjects will apply sufficient study drug to cover completely each lesion with a thin layer of study drug and will record the time of study drug application in a daily diary provided by the study site. Note that subjects are allowed, but not required, to treat palms, fingernails, soles, toenails, and scalp plaques with study drug. If a subject chooses to treat plaques on palms, fingernails, soles, toenails, and/or scalp, they should do so for the entirety of the treatment period from Day 1 to Day 29. Subjects will be instructed to apply study drug in the morning throughout the entirety of their participation in the study. At the phone contacts at Days 8 and 22, subjects should be reminded to complete their daily diary and bring it with them to the next clinic visit.

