### 11. PHARMACOKINETIC ANALYSES

Unless otherwise specified below, missing sampling or concentration values should not be imputed, but left missing in the calculation of derived PK parameters. If the actual sampling time is missing, but a valid concentration value has been measured, the scheduled protocol time will be used for the calculation of derived PK parameters. A missing pre-dose value will be set to 0 for the PK calculations corresponding to an observation at dosing time.

All pharmacokinetic (PK) analyses and generation of the tables, figures, and listings (TFLs) will be performed using a validated installation of Phoenix WinNonlin® version 8.1 ( ) as part of a 21 CFR Part 11 compliant database system (Pharsight Knowledge Database "PKS").

Blood samples for the analysis of tapinarof and its metabolite, tapinarof sulfate, will be collected pre-dose and post dose on Day 1 and Day 2 (Visits 3 and 4) as well as Day 29 and Day 30 (Visits 6 and 7) at 1, 2, 3, 4, 5, 8, 12, and 24 hours after dosing. On Day 15 (Visit 5), samples will be collected pre-dose and at 2- and 4-hours post dose ( $\pm 10$  mins). Samples collected outside the pre-determined intervals will be flagged and footnoted.

PK data from the PK population will be presented in listings. Plasma concentrations will be summarized using descriptive statistics. The number of plasma samples that were BQL will be summarized by subject and overall.

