PK parameter estimates for tapinarof and its metabolite tapinarof sulfate on Day 1 and Day 29 will be calculated using non-compartmental analysis (NCA) of the plasma concentration versus time data utilizing actual sample collection time. NCA will be conducted using validated PK data analysis software (Phoenix WinNonlin version 8.1). AUC values will be estimated using the linear up-log down method. A minimum number of 3 data points are required for determination of AUC. The apparent first-order terminal elimination rate constant ( $\lambda_z$ ) will be calculated as the negative of the slope from linear regression of the semi-log concentration-time curve during the terminal phase. The apparent first-order terminal elimination half-life,  $t_{1/2}$ , will be calculated as  $0.693/\lambda_z$ . A minimum of three descending concentration-time points, excluding the Cmax, above the lower limit of quantification (LLOQ) will be used in the estimation of the terminal phase rate constant ( $\lambda_z$ ), for the determination of the terminal half-life ( $t_{1/2}$ ). PK parameter estimates are listed in Table 1, other parameters can be added, if data permits.

PK parameters Cmax and  $AUC_{0-\tau}$  will also be normalized to %BSA treated by dividing each parameter by cm^2 of body surface area of disease. For this calculation, 1% BSA is equal to 185 cm^2.

Imputation of BQL data should be addressed as follows:

- If a BQL value occurs in a profile before the first measurable concentration, it will be assigned a value of zero concentration. Therefore, a subject with BQL values for the entire dosing interval will have a Cmax of zero.
- If a BQL value occurs after a measurable concentration in a profile and is followed by a value above the lower limit of quantitation (LLOQ), then BQL should be treated as 'missing'.
- If a BQL value occurs at the end of the collection interval (after the last quantifiable concentration) it will generally be treated as 'missing'
- If two BQL values occur in succession after Cmax, the profile will be deemed to have terminated at the first BLQ value and any subsequent concentrations will be omitted from pharmacokinetic calculations and individual plots, which are to reflect data that were used in the NCA, but will be maintained in concentration-time tables and plots of mean data

BQL values will be treated as zero for summary statistics tables or mean figures.

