**Table 1: PK Parameters and Definitions** 

Parameter	Description of Parameter
$C_{max}$	The maximum observed concentration of tapinarof and its metabolite tapinarof sulfate measured after dosing
$T_{\text{max}}$	Time at which the Cmax is observed.
$AUC_{0\tau}$	The area under the tapinarof and its metabolite tapinarof sulfate concentration versus time curve from time zero to the end of the dosing period
$t_{1/2}$	Apparent first-order terminal elimination half-life of tapinarof and its metabolite tapinarof sulfate

Individual PK parameter estimates from non-compartmental analysis, sorted by Day, will be listed for all individuals and will include tapinarof and its metabolite tapinarof sulfate.

[figure not shown]
PK parameters for tapinarof and its metabolite tapinarof sulfate will be summarized separately and will include the count, mean, geometric mean, standard deviation, CV%, median, min, max and geometric CV% range.

Individual Day 1 and Day 29 time-concentration graphs for tapinarof and its metabolite tapinarof sulfate will be provided for each subject in both linear and semi-log scales. Actual sampling times will be used for individual plots. Overlaid individual concentration-time plots by Day for tapinarof and its metabolite tapinarof sulfate will be provided in linear and semi-log scale. Mean concentration-time graphs by Day for tapinarof and its metabolite tapinarof sulfate will be provided in both linear and semi-log scales.

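### SAP 11 sets a missing pre-dose concentration to zero on Day 29 as well as Day 1, which lowers that subject's Day 29 AUC if the true trough is quantifiable

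*SAP*

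**What the plan says.** SAP 11 opens with a default for missing PK data: "Unless otherwise specified below, missing sampling or concentration values should not be imputed, but left missing in the calculation of derived PK parameters". Two sentences later comes a specific rule for one sample: "A missing pre-dose value will be set to 0 for the PK calculations corresponding to an observation at dosing time". That rule names no study day.

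The same section derives non-compartmental parameters for both compounds on Day 1 and Day 29. Samples are taken pre-dose and "at 1, 2, 3, 4, 5, 8, 12, and 24 hours after dosing". On the method, "AUC values will be estimated using the linear up-log down method". SAP Table 1 defines AUC0-τ as the area under the "concentration versus time curve from time zero to the end of the dosing period", which is 24 hours here. AUC needs at least 3 data points. A BQL value before the first measurable one is set to zero, and a BQL value at the end of the interval is generally treated as missing.

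On dosing, Protocol 3.1 says "subjects will apply tapinarof cream, 1% to affected areas once a day for 29 days". Protocol 1.2 adds: "The 29-day treatment phase was selected to ensure steady-state is achieved". It also expects tapinarof to fall to undetectable or close to it after several weeks, and reports no accumulation in earlier studies.

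**The concern.** On Day 1 a pre-dose concentration of zero needs no data, because no drug has been given. That reasoning does not carry over to Day 29. A compliant subject has had 28 applications by then (29 daily doses less the one still to come), so the pre-dose value is a trough. It may be low, but prior dosing means zero can no longer be assumed.

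Day 29 AUC0-τ is one of the PK parameters under the primary objective (Protocol 2, SAP 3.1). The study is a maximal-use trial meant to show exposure when absorption is at its greatest (Protocol 1.1.2). A fill-in rule that can leave AUC unchanged or too low, but never too high, is a poor default there. The AUC normalised to treated area (SAP 11) carries the same proportional error.

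**Working it through.** The plan gives no figure to reproduce, and no concentrations, quantification limit or missing-sample rate. The sampling times, AUC method and 24-hour interval come from SAP 11 and SAP Table 1. All profile shapes below are assumptions.

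**Direction.** Write C0 for the true pre-dose value and C1 for the 1-hour value. Only the 0-1 h segment changes.

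- With C0 replaced by 0, the segment is linear-up: 0.5 × C1.
- If C1 ≥ C0, the true segment is 0.5 × (C0 + C1), so the loss is 0.5 × C0.
- If C1 < C0, the true segment is (C0 − C1) / ln(C0/C1). This exceeds C1, so the loss exceeds 0.5 × C1.
- If C0 is BQL, it would have been set to 0 under the leading-BQL rule anyway, so the loss is 0.

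The error is therefore downward or nil. As a share of AUC, the C1 ≥ C0 case is 0.5 × C0 / AUC0-24.

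**Size in one affected subject, profile running to 24 h.** The humped profiles are C(t) = f + (1 − f) × h(t), with h = 0, 0.4, 0.7, 0.9, 1, 0.95, 0.7, 0.45, 0 at 0, 1, 2, 3, 4, 5, 8, 12, 24 h. Here f is the trough as a fraction of Cmax.

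| Assumed profile | True AUC0-24 | Loss | Error |
|---|---|---|---|
| Trough BQL | any | 0 | 0% |
| Hump, f = 0.05 | 10.66 | 0.5 × 0.05 = 0.025 | -0.2% |
| Hump, f = 0.10 | 11.58 | 0.5 × 0.10 = 0.05 | -0.4% |
| Hump, f = 0.25 | 13.90 | 0.5 × 0.25 = 0.125 | -0.9% |
| Hump, f = 0.50 | 17.38 | 0.5 × 0.50 = 0.25 | -1.4% |
| Another shape, trough 1, peak 2 | 31.78 | 0.5 × 1 = 0.5 | -1.6% |
| Flat at 1 | 24.00 | 0.5 × 1 = 0.5 | -2.1% |
| Pre-dose 2, then flat at 1 | 1/ln 2 + 23 = 24.44 | 1.44 − 0.5 = 0.94 | -3.9% |
| Pre-dose 3, then flat at 1 | 2/ln 3 + 23 = 24.82 | 1.82 − 0.5 = 1.32 | -5.3% |

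**Profiles cut short by BQL values.** Assume a flat profile to the last quantifiable time Tlast, with AUC taken to Tlast. The share lost is 0.5 / Tlast: 25% at 2 h, 10% at 5 h, 4.2% at 12 h. The percentage is large because the AUC is small.

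**Effect on the mean.** For 20 equal flat profiles, one missing sample moves the arithmetic mean by 2.08% / 20 = 0.1%. Five missing samples move it by 0.5%.

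**What does not move.** SAP Table 1 defines Cmax as the maximum measured after dosing, so a pre-dose fill-in cannot change it.

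**Alternatives to zero.**

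- *Use the subject's own 24-hour value.* The error is 0% whenever C0 = C24. In the two profiles with a high pre-dose value, the first segment becomes 1 and AUC becomes 24. The errors are 24/24.44 − 1 = -1.8% and 24/24.82 − 1 = -3.3%, against -3.9% and -5.3% under zero.
- *Delete the rule and leave the value missing.* If the first hour is then not counted, the retained area is 0, against 0.5 × C1 under the zero rule. This is worse whenever C1 is above zero. The flat profile, for example, loses 1/24 = 4.2% instead of 2.1%.

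**The case against.** The strongest reply is that the protocol does not expect a Day 29 trough worth imputing. Protocol 1.2 predicts undetectable or nearly undetectable tapinarof by then. A BQL pre-dose value would be set to zero anyway, so in the expected case the rule changes nothing. This stands as a limit on the point but does not dispose of it. The prediction comes from earlier studies, and Protocol 1.2 itself says that patients with disease this extensive had not been studied. It is made for tapinarof, and no expected trough is given for the sulfate.

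Some stronger readings are tempting, but the documents do not support them.

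- A reader might infer that the rule contradicts the default of leaving missing values missing. It does not: the default opens by allowing for exceptions stated below it, and this is one.
- A reader might infer that Day 29 AUC is biased as a matter of course. The error needs both a missing pre-dose sample and a quantifiable true trough.
- A reader might infer that the study's peak exposure is understated. SAP Appendix D, section 6, expects the highest mean Cmax on Day 1, where zero is correct. PK results are summarised descriptively by day, and no formal Day 1 to Day 29 test is planned.
- A reader might conclude that AUC should be withheld when the 24-hour value is also missing. SAP 11 generally treats a terminal BQL value as missing, so withholding could drop low-exposure subjects selectively. It would also override the 3-point minimum.

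**Conclusion.** The point holds as a minor, conditional defect in a stated rule. The zero rule reaches Day 29, where prior dosing removes its justification, and any error it causes in AUC0-τ is downward. For a profile quantifiable to 24 hours and rising or level after the dose, the loss per affected subject runs from 0% (BQL trough) to about 2% (flat). It is larger with a high pre-dose value or a truncated profile. The effect on the mean of about 20 subjects is around 0.1% per missing sample for flat profiles. These sizes rest on assumed profiles and nominal sampling times. How often the Day 29 pre-dose sample will be missing is unknown. The change is worth making because it is cheap and the error runs only one way. It is not a threat to the study's conclusions.

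**What to change.** In SAP 11, limit the zero rule to Day 1 and add a Day 29 rule:

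- Replace a missing Day 29 pre-dose concentration with the same subject's assayed 24-hour (Day 30) concentration.
- If that 24-hour sample was assayed and is BQL, use 0. State this explicitly, because the terminal-BQL rule would otherwise make it missing.
- If no 24-hour sample was assayed, keep zero, flag the profile in the listing, and calculate AUC under the existing 3-point minimum.

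The SAP should also say whether an imputed value counts toward the 3 points, which it does not do now.

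The cost is a few sentences in SAP 11. The 24-hour sample is already scheduled. The downside is that the 24-hour value may differ from the true pre-dose value. If levels are still declining, some underestimate remains, as in the -1.8% and -3.3% cases above. Where the 24-hour value is BQL, the result is the same as under the current rule, so the fix does not help profiles cut short by BQL values.

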4. STUDY POPULATION

4.1. Type and Number of Subjects

Approximately 20 adult subjects with extensive plaque psoriasis will be enrolled in the study at approximately 6 sites in the US.

Protocol violations from inclusion and exclusion criteria are prohibited because ineligible study subjects can potentially jeopardize the scientific integrity of the study, regulatory acceptability, or subject safety. Therefore, adherence to the criteria as specified in the protocol is essential.

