4.2. Inclusion Criteria

Each subject must meet all of the following criteria to be eligible to participate in the study:

- 1. Male and female subjects ages 18 to 75 years with confirmed clinical diagnosis of chronic psoriasis and stable disease for at least 6 months prior to the study;
- 2. BSA involvement ≥ 20% (the subject's scalp, palms, and soles should be excluded from the %BSA calculations to determine eligibility at Screening);
- 3. A PGA score of ≥ 3 at Screening;
- 4. WOCBP and male subjects who are engaging in sexual activity that could lead to pregnancy must use at least 1 of the following adequate birth control methods while on study and for 4 weeks after the last exposure to study drug. Acceptable contraception methods are:
 - Male or male partner with vasectomy, OR
 - Male condom AND partner use of one of the contraceptive options below:
 - Spermicide;
 - Contraceptive subdermal implant that meets effectiveness criteria including a < 1% rate of failure per year, as stated in the product label;
 - Intrauterine device or intrauterine system that meets effectiveness criteria including a < 1% rate of failure per year, as stated in the product label;
 - Oral contraceptive, either combined or progestogen alone;
 - Injectable progestogen;
 - Contraceptive vaginal ring;
 - Percutaneous contraceptive patches.

Note: Subjects using hormonal contraceptives must have been on a stable dose for at least 4 weeks before Baseline.

These allowed methods of contraception are only effective when used consistently, correctly, and in accordance with the product label. The Investigator is responsible for ensuring that subjects understand how to properly use these methods of contraception.

Non-childbearing potential is defined as premenarchal; pre-menopausal females with a documented bilateral tubal ligation, bilateral oophorectomy (removal of the ovaries) or hysterectomy; or hysteroscopic sterilization; or postmenopausal females defined as a cessation of menses for at least 12 months without an alternative medical cause. In questionable cases a blood sample with simultaneous follicle-stimulating hormone

(FSH) > 40 mIU/mL is confirmatory. Documented verbal history from the subject is acceptable.

Subjects who are abstinent are eligible, but they must agree to use one of the birth control methods listed above if they start engaging in sexual activity that could lead to pregnancy during the study.

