6.3.2. Brief Physical Exam

A brief physical examination will include, at a minimum, assessments of the skin, lungs, CV system, and abdomen (liver and spleen). Height and weight will be measured at Screening only. Investigators should pay special attention to clinical signs related to previous serious illness.

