APPENDIX 1. PHYSICIAN GLOBAL ASSESSMENT

Each assessment should be made as a visual 'average' of the severity of all treated areas at the time of the assessment.

Scoring should not be influenced by extent of plaques, participant symptoms, or impact on participant's quality of life.

Score/Grade Description		Description	
0	Clear	No signs of psoriasis; post-inflammatory hyperpigmentation may be present	
1	Almost clear	No thickening; normal to pink coloration; no to minimal focal scaling	
2	Mild	Just detectable to mild thickening; pink to light red coloration; predominantly fine scaling	
3	Moderate	Clearly distinguishable to moderate thickening; dull to bright red, clearly distinguishable erythema; moderate scaling	
4	Severe	Severe thickening with hard edges; bright to deep dark red coloration; severe/coarse scaling covering almost all or all plaques	

APPENDIX 2. CALCULATION OF PERCENT BODY SURFACE AREA AFFECTED AND PSORIASIS AREA AND SEVERITY INDEX

The %BSA affected and PASI will be calculated using the following regional body areas:

- Head and neck
- Trunk, includes internal axillae and groin
- · Upper extremities, includes arms, external axillae, and hands
- Lower extremities, includes legs, buttocks, and feet

Note: At Screening, Baseline and for all efficacy assessments, plaques on scalp, palms, fingernails, toenails, and soles will not be included in the calculation of %BSA affected as these areas will not be included in the efficacy analyses.

Complete the %BSA assessment before the PASI.

Calculation of %BSA Affected:

Measurement of involved BSA is estimated by the handprint method: the total palmar surface of the subject's palm and digits is approximately 1% of their total BSA.

Estimate the involved regional area by determining the number of "full" handprints plus the number of handprints covered if several smaller plaques are "pushed together." Each region can have up to 100% involvement.

- Head and neck = 10% of overall BSA (10 handprints);
 1 hand-sized plaque ~ 10% of head and neck area
- Upper extremities = 20% of overall BSA (20 handprints);
 1 hand-sized plaque ~ 5% of the upper extremities

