### 8.4 Demographic and Baseline Characteristics

Demographic variables include age, sex, ethnicity, race, height, weight, and body mass index (BMI). Age will be calculated in years relative to the informed consent date. Baseline characteristics include physician global assessment (PGA), percent body surface area affected (%BSA), and psoriasis area and severity index (PASI) score.

Demographic and baseline characteristics as well as medical history will be summarized using the safety analysis set. In addition, demographic and baseline characteristics as well as medical history will be listed by subject.

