14.3.4.1.1	Summary of Clinical Laboratory Results, Change from Baseline - Hematology (Safety Analysis Set)
14.3.4.1.2	Summary of Clinical Laboratory Results, Shift from Baseline - Hematology (Safety Analysis Set)
14.3.4.2.1	Summary of Clinical Laboratory Results, Change from Baseline - Chemistry (Safety Analysis Set)
14.3.4.2.2	Summary of Clinical Laboratory Results, Shift from Baseline - Chemistry (Safety Analysis Set)
14.3.4.3.1	Summary of Clinical Laboratory Results, Change from Baseline - Urinalysis (Safety Analysis Set)
14.3.4.3.2	Summary of Clinical Laboratory Results Shift from Baseline - Urinalysis (Safety Analysis Set)
14.3.4.4.1	
14.3.5.1.1	Summary of Vital Signs - Change from Baseline (Safety Analysis Set)
14.3.5.1.2	Summary of Vital Signs - Shift from Baseline (Safety Analysis Set)
14.3.5.2.1	Local Tolerability Scale Assessments - Overall Dryness, Erythema, Peeling (Safety Analysis Set)
14.3.5.2.2.1	Local Tolerability Scale Assessments, Sensitive Areas Treated - Face (Safety Analysis Set)
14.3.5.2.2.2	Local Tolerability Scale Assessments, Sensitive Areas Treated - Neck (Safety Analysis Set)
14.3.5.2.2.3	Local Tolerability Scale Assessments, Sensitive Areas Treated – Skin Folds (Safety Analysis Set)
14.3.5.2.2.4	Local Tolerability Scale Assessments, Sensitive Areas Treated – Axilla (Safety Analysis Set)

[figure not shown]
ICH Table Number   Table Title	Table Title
14.3.5.2.2.5	Local Tolerability Scale Assessments, Sensitive Areas Treated - Inframammary (Safety Analysis Set)
14.3.5.2.2.6	Local Tolerability Scale Assessments, Sensitive Areas Treated – Anal Crux (Safety Analysis Set)
14.3.5.2.2.7	Local Tolerability Scale Assessments, Sensitive Areas Treated - Genitalia (Safety Analysis Set)
14.3.5.3.1-	<ecg from="" tables="">></ecg>
14.3.5.3.13	
14.3.5.4.1	Summary Statistics of Tapinarof Concentrations by Day and Time (PK Analysis Set)
14.3.5.4.2	Summary Statistics of Tapinarof Sulfate Concentrations by Day and Time (PK Analysis Set)
14.3.5.4.3	Number and Percent of Subjects with Concentrations Below the Limit of Quantification (BQL) (PK Analysis Set)
14.3.5.4.4	Summary Statistics of PK Parameter Estimates for Tapinarof by Day (PK Analysis Set)
14.3.5.4.5	Summary Statistics Normalized PK Parameter Estimates (by body surface area treated) for Tapinarof by Day (PK
	Analysis Set)
14.3.5.4.6	Summary Statistics of PK Parameter Estimates for Tapinarof Sulfate by Day (PK Analysis Set)

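### SAP 11 labels normalised Cmax and AUC0-τ as per cm², but one fixed constant (1% BSA = 185 cm²) for every subject makes them per-%BSA values in other units

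*SAP*

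**What the plan says.** SAP 11 (Pharmacokinetic Analyses) adds a normalised version of two PK parameters. Cmax and AUC0-τ "will also be normalized to %BSA treated by dividing each parameter by cm"² of diseased body surface, and "For this calculation, 1% BSA is equal to 185 cm"². The SAP gives no source for the constant, makes no adjustment for body size, and lists no references in its section 13.

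The outputs are Tables 14.3.5.4.5 ("Summary Statistics Normalized PK Parameter Estimates (by body surface area treated) for Tapinarof by Day") and 14.3.5.4.7 (the same for tapinarof sulfate), with Listings 16.2.9.10 and 16.2.9.12.

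Protocol Appendix 2 defines how %BSA is scored. It uses the handprint method, in which "the total palmar surface of the subject's palm and digits is approximately 1% of their total BSA". One per cent is thus one per cent of that subject's own surface.

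Body size is recorded. Protocol 6.3.2 states that "Height and weight will be measured at Screening only", and SAP 8.4 lists both among the demographic variables. The eligibility criteria (Protocol 4.2 and 4.3) set no weight, height or BMI limit.

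**The concern.** The %BSA score is relative to the individual, but its conversion to area is not. A small adult and a large adult who both score 30% have different areas of affected skin, yet the SAP gives both 30 × 185 = 5,550 cm². Dividing by a constant only changes the units of a per-%BSA figure, while the cm² unit tells the reader that a real skin area was used.

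At stake is how four planned outputs are read. They are the PK outputs that relate plasma exposure to skin area. A reader of this maximal-use study could take a listed value as exposure per cm² of that subject's skin, or compare it with a per-cm² figure derived from actual areas elsewhere. Neither reading would be valid.

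**Working it through.** **Inputs from the documents**
- 185 cm² per 1% BSA (SAP 11).
- %BSA scored against the subject's own total surface (Protocol Appendix 2).
- Minimum involvement at Screening: "BSA involvement ≥ 20"% (Protocol 4.2).
- About 20 subjects (Protocol 4.1).

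**Inputs assumed, not in the documents**
- Heights, weights and BSA distributions.
- The Mosteller formula, BSA (m²) = √(height cm × weight kg / 3600), with DuBois as a check.

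**Step 1. What the constant implies.** 185 × 100 = 18,500 cm² = 1.85 m² for every subject.

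**Step 2. Size of the error.** Let P be the PK parameter, b the scored %BSA and A the subject's own BSA in m². One per cent of A is 100 × A cm².
- SAP value: P / (b × 185)
- Value using the subject's own area: P / (b × 100 × A)
- Ratio of the first to the second: 100A / 185 = A / 1.85

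The %BSA cancels, so the relative error is A/1.85 − 1 and depends only on body size.

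**Step 3. Illustrative subjects (assumed, Mosteller).**

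| Height / weight | BSA (m²) | Error of SAP value |
|---|---|---|
| 155 cm / 52 kg | 1.50 | -19% |
| 160 cm / 60 kg | 1.63 | -12% |
| 170 cm / 72 kg | 1.84 | about 0% |
| 175 cm / 80 kg | 1.97 | +7% |
| 180 cm / 100 kg | 2.24 | +21% |
| 185 cm / 120 kg | 2.48 | +34% |
| 188 cm / 130 kg | 2.61 | +41% |

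DuBois gives -19% and +37% for the first and last rows. An error of exactly -20% needs A = 0.80 × 1.85 = 1.48 m², and exactly +40% needs 1.40 × 1.85 = 2.59 m².

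In area terms, at the 20% entry threshold the SAP uses 20 × 185 = 3,700 cm². The subject's own area would be 3,000 cm² at 1.5 m² and 5,200 cm² at 2.6 m².

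**Step 4. Typical rather than extreme subjects (assumed normal distributions of BSA).**
- Mean 1.85, SD 0.20: the middle 90% run from 1.85 − 1.645 × 0.20 = 1.52 to 2.18 m², an error of about -18% to +18%. The average error is nil.
- Mean 2.05, SD 0.25: the middle 90% run from 1.64 to 2.46 m², an error of about -11% to +33%. The average factor is 2.05/1.85 = 1.11. Simulating groups of 20, the smallest and largest errors average about -14% and +36%.

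**Step 5. What does not change.**
- Dividing every value by 185 scales mean and SD alike, so CV% and subject ranking are those of a per-%BSA normalisation.
- Height and weight are taken once, so A/1.85 is the same on Day 1 and Day 29 and cancels in a within-subject ratio.
- Un-normalised Cmax, AUC0-τ, tmax and t½ do not use the constant.

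**The case against.** The strongest reply is that SAP 11 also says the parameters are normalised to %BSA. On that reading 185 is a printed scale factor, and only the unit label misleads. This stands in part, and it is why relabelling is an acceptable remedy. It does not remove the point, because the same sentence names an area in cm² as the divisor and the rule does not deliver one.

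Three stronger readings are tempting, and the documents do not support them.

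- **That every subject's value is wrong by -20% to +40%.** Those are the ends of an assumed range. No body-size distribution is given, and a subject near 1.85 m² has almost no error. The BSA formulas are themselves approximations, as is the handprint estimate.
- **That the constant inflates the reported CV%.** The direction is unknown. Cmax and AUC are plasma measures, and larger subjects may also have larger distribution volume and clearance. Suppose, as an illustration, equal absorption per cm² with volume and clearance proportional to BSA. Two subjects with equal %BSA would then have equal Cmax. The SAP's figure would show them as equal, and an individual per-cm² figure would separate subjects of 1.5 and 2.6 m² by 2.6/1.5 = 1.73-fold. The documents give no scaling that would settle this.
- **That the main result of a maximal-use study is compromised.** The primary PK endpoints are un-normalised. The normalised values appear only in the SAP, are descriptive, and carry no hypothesis or decision rule.

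It is also fair to say that PK parameters, %BSA, height and weight are planned for listing by subject, so the figure could be recomputed. That limits the harm, but the planned tables would still be mislabelled.

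**Conclusion.** The point holds in a limited form. SAP 11 promises division by cm² of diseased skin and, through one constant, delivers a per-%BSA value in other units. Relative to the subject's own area as scored, each value is off by (own BSA)/1.85. That factor follows from the documents alone.

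Its size does not. About -20% to +40% applies only at the extremes of an assumed BSA range of 1.5 to 2.6 m². Under the two assumed distributions the middle 90% of subjects lie within about -18% to +18%, or -11% to +33%. The reported CV% may differ in either direction from that of a true per-cm² figure.

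The error is confined to two tables and two listings, with no effect on the primary PK endpoints or on within-subject Day 1/Day 29 comparisons. It is worth correcting because it affects reported numbers and costs little. It does not threaten the study's conclusions. Whether the area should be the treated or the diseased skin is a separate question and is not judged here.

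**What to change.** Amend SAP 11 in one of two ways, according to what is intended.

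1. **If exposure per cm² is wanted:** replace the constant with 1% BSA (cm²) = 100 × individual BSA (m²). Derive BSA from Screening height and weight by a named formula, for example Mosteller, √(height cm × weight kg / 3600). Use it for Tables 14.3.5.4.5 and 14.3.5.4.7 and Listings 16.2.9.10 and 16.2.9.12.
2. **If only a per-%BSA normalisation is wanted:** drop the 185 factor and label those outputs per 1% BSA, with no cm² unit.

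The first option costs one SAP sentence and one derived variable, and it relies on an approximate BSA formula. The second costs a change of wording and labels. Neither needs new data or a protocol amendment, because the protocol's PK analysis section (10.4.4) does not mention the normalisation.
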